3.2. Therapeutic Trial

Patients who have positive detection of ctDNA on or before their 12 month ctDNA surveillance assessment will be allocated to pembrolizumab treatment within the therapeutic trial centrally by ICR-CTSU.

Prior to the implementation of protocol v6.0 during the randomised component of the trial, patients who had positive detection of ctDNA on or before their 12 month ctDNA surveillance assessment were randomised centrally by ICR-CTSU in a 2:1 ratio to pembrolizumab treatment or observation (continued blinded ctDNA surveillance).

All patients randomised to observation prior to implementation of protocol v6.0 who remain in ctDNA surveillance, will transition to the non-randomised trial component following re-consent, and be allocated to pembrolizumab at the next positive ctDNA result.

3.2.1. Pembrolizumab treatment group

If a patient is allocated to the pembrolizumab treatment group, the treating team will be informed by ICR-CTSU. If the patient is receiving adjuvant capecitabine or radiotherapy, they will be offered the option to join the therapeutic trial either by switching treatment from capecitabine to pembrolizumab, or commencing pembrolizumab in combination with radiotherapy. If the patient confirms their consent to receive trial treatment (including switching their treatment from capecitabine to pembrolizumab) staging scans should be done to detect for evidence of macroscopic disease, prior to commencing pembrolizumab. If macroscopic disease is detected, the patient will not receive pembrolizumab treatment and will instead receive standard treatment for recurrent disease outside of the c-TRAK TN trial. If there is no evidence of macroscopic disease, the patient should commence treatment with pembrolizumab treatment (200mg given intravenously every 3 weeks) for up to a maximum of 12 months or until unacceptable toxicity or withdrawal of the patient's consent for any reason (see section 11.6). No further imaging will be performed after commencing pembrolizumab unless clinically indicated, in which case local procedure should be followed. Patients who are diagnosed with disease recurrence must stop pembrolizumab, and should receive standard treatment for recurrent disease outside of the c-TRAK TN trial. Patients who present with isolated lymphadenopathy may continue pembrolizumab until relapse is confirmed, and should be managed as per section 13.1.

Patients who are allocated to pembrolizumab but do not wish to commence pembrolizumab treatment (including switching treatment from capecitabine to pembrolizumab), will not enter the therapeutic component of the c-TRAK TN trial and if agreed should instead continue with 3 monthly ctDNA surveillance. Blood samples for ctDNA analysis should continue to be collected during and after pembrolizumab treatment as described in section 11. The results of these ctDNA analyses will not be reported to the treating team or patient.

3.2.2. **Observation group (continued blinded ctDNA surveillance – prior to protocol v6.0)**

Prior to the implementation of protocol v6.0 during the randomised component of the trial, if a patient was randomised to the observation group, the treating team and patient were **not** informed that randomisation had taken place in order to remain blinded to the positive ctDNA result the patient would continue to have blood samples collected for ctDNA analysis as described in section 8.

Following implementation of protocol v6.0, all patients who were previously randomised to observation and remain in ctDNA surveillance will transition to the non-randomised component of the trial following reconsent, and be allocated to pembrolizumab at the next positive ctDNA result.

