In the proposed c-TRAK TN study we will personalise each ctDNA assay to the mutations identified in each patients' tumour, and the assays will therefore not be CE marked. The detection of MRD in haematological malignancies is routinely done with non-CE marked assays, as the assays are designed to the rearrangements identified in an individual patients' leukaemia. All assays will be manufactured at the c-TRAK TN central laboratory and used on the premises of manufacture, in accordance with the Guidance on the In Vitro Diagnostic Medical Devices Directive 98/79/EC (August 2013). All assays will be subject to strict validation prior to use.

Rationale for protocol amendments to reduce the time between surgery and the start of ctDNA surveillance – May 2019 (protocol v5.0)

In protocol version 5.0 the permitted time from surgery to registration in the trial was reduced, to reflect the risk of very early relapse of patients with triple negative breast cancer [18], and to maximize the opportunity for patients to be able to start ctDNA surveillance prior to clinical relapse. In addition, the trial was amended to allow patients to start ctDNA surveillance before or during standard adjuvant radiotherapy, to reduce the time from surgery to starting ctDNA surveillance. In some patients this may result in patients starting pembrolizumab concurrent with adjuvant radiotherapy, similar to other trials in the post-neoadjuvant

therapy setting for example where adjuvant trastuzumab-emtansine is given concurrent with adjuvant radiotherapy [19]. In addition, the trial was amended to allow patients who have completed neoadjuvant chemotherapy, and are then receiving adjuvant capecitabine, to start ctDNA surveillance after 3 months capecitabine [18], as otherwise patients have a long delay between surgery and the start of ctDNA surveillance (refer to section 5.4.1 for details).

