2. TRIAL OBJECTIVES

2.1. Primary Objectives

- To assess whether digital PCR ctDNA assays, as a non-invasive biomarker on serial blood samples, can predict which patients are at highest risk of relapse and identify patients with minimal residual disease not visible on imaging.
- To assess whether pembrolizumab results in a sustained clearance of ctDNA in patients who have completed treatment for moderate or high risk early stage triple negative breast cancer, but have minimal residual disease (MRD) detected by serially assessed ctDNA analysis.

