commence ctDNA surveillance 3 months (+/- 2 weeks) after starting capecitabine and treatment can continue while ctDNA surveillance is ongoing. Patients who have stopped capecitabine prior to completing 3 months of treatment for any reason other than disease recurrence are also permitted to start ctDNA surveillance. Patients may start ctDNA surveillance prior to, and during, adjuvant radiotherapy.

Blood samples for ctDNA analysis should be collected every 3 months for up to two years from starting ctDNA surveillance and sent to the c-TRAK TN central laboratory for processing and analysis. DNA extracted from plasma will be analysed for the presence of ctDNA, and assayed as positive (ctDNA detected) or negative (ctDNA not detected). All positive ctDNA results within 12 months of a patient starting ctDNA surveillance will be notified to the ICR-CTSU in order for allocation to the therapeutic trial to be performed independently of the recruiting site.

If after the first 12 months of ctDNA surveillance, patients have not had a positive ctDNA result they will continue to have ctDNA surveillance every 3 months up to 2 years from starting ctDNA surveillance. All ctDNA blood samples collected in the second year of surveillance are exploratory, to confirm the optimal duration of ctDNA surveillance, and whether in subsequent studies two years of active surveillance as opposed to one year should be adopted. These samples will not be analysed in real-time. The exception to this is for patients who have missed blood samples within the first 12 months as a result of ctDNA surveillance suspension. For these patients real-time ctDNA testing, and allocation to trial treatment, may be extended beyond the original 12 months for a proportional amount of time to counteract the loss of surveillance samples for each patient.

Approximately 50% of patients entered into ctDNA surveillance will have moderate risk disease. The IDMC will monitor the proportional split of high/moderate risk patients as recruitment progresses and may recommend a cap to entry of moderate risk patients if the proportion materially exceeds 50%.

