9.2.2. Exclusion Criteria

1) Any concurrent or planned anti-cancer treatment since completing standard therapy for early stage triple negative breast cancer other than loco regional adjuvant radiotherapy or standard adjuvant chemotherapy, or a permitted bisphosphonate/denosumab.

- 2) Diagnosis of an additional cancer since enrolment in the trial other than basal cell carcinoma of the skin or cervical carcinoma in situ.
- 3) Prior chemotherapy, targeted small molecule therapy or radiation therapy within 4 weeks prior to first administration of pembrolizumab, with the exception of planned loco regional adjuvant radiotherapy.
- 4) Prior anti-cancer monoclonal antibody (mAb) within 4 weeks prior to first administration of pembrolizumab.
- 5) Has not recovered (≤ Grade 1 or patient's baseline) from adverse events due to a previously administered therapy. Note: Patients with ≤ grade 2 neuropathy or alopecia of any grade are an exception to this criterion and may qualify for the trial. If patient received major surgery, they must have recovered adequately from the toxicity and/or complications from the surgery prior to allocation.
- 6) Treatment with an unlicensed or investigational product within 4 weeks prior to first administration of pembrolizumab.
- 7) Active autoimmune disease requiring systemic therapy in the last 2 years (i.e. with use of disease modifying agents, corticosteroids or immunosuppressive drugs). Replacement therapy (e.g. thyroxine, insulin or physiologic corticosteroid replacement therapy for adrenal or pituitary insufficiency) is not considered a form of such systemic treatment.
- 8) Diagnosis of immunodeficiency or is receiving systemic steroid therapy or any other form of immunosuppressive therapy within 7 days prior to the first administration of pembrolizumab.
- 9) Known history of active Tuberculosis Bacillus (TB).
- 10) Known history of Human Immunodeficiency Virus (HIV).
- 11) Known active Hepatitis B or Hepatitis C.
- 12) Known history of, or any evidence of active, non-infectious pneumonitis.
- 13) Active infection requiring systemic therapy.
- 14) Previous solid organ or allogenic stem cell transplantation.
- 15) Received a live vaccine within 30 days of planned start of pembrolizumab (seasonal flu vaccines are generally inactivated and are permitted; however intranasal influenza vaccines (e.g. Flu-Mist) are live attenuated vaccines and are not permitted).

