9.3. Procedure for confirming patient eligibility to start pembrolizumab treatment

If the patient is confirmed eligible to start pembrolizumab treatment, then treatment should commence within a maximum of 4 weeks of the date when the recruiting site was first notified about the treatment allocation. For patients who are switching treatment from capecitabine to pembrolizumab, a washout period of 4 weeks must be observed prior to starting trial treatment. This period may be extended if delays are

encountered for practical reasons including those caused by the COVID 19 pandemic and the patient remains eligible per protocol, please discuss such cases with the ICR-CTSU trial team.

Patients who are ineligible to start treatment due to macroscopic disease identified on pre-treatment imaging will not receive treatment within the c-TRAK TN trial and will instead be treated as per local guidelines for metastatic disease/recurrence. No further blood samples for ctDNA analysis should be collected.

Patients who do not meet the eligibility criteria (for reasons other than disease recurrence) or do not wish to receive pembrolizumab treatment, should continue to have bloods taken for ctDNA surveillance every 3 months for up to 2 years from starting ctDNA surveillance. Patients should then be followed up for disease recurrence detection as described in section 11.5.

The **pre-treatment eligibility checklist** must be completed for all patients allocated to pembrolizumab treatment to confirm patient consent and eligibility and the planned start date of treatment (where applicable). The pre-treatment eligibility checklist should be completed within 4 weeks of when the recruiting site was first notified about the treatment allocation. Written confirmation that eligibility has been assessed by an investigator and confirmation of the patient's consent and the informed consent process should be documented in the patient's medical records.

For patients confirmed eligible, pembrolizumab treatment should commence as soon as possible and within a maximum of 4 weeks from when the recruiting site was first notified about the treatment allocation. As stated above, for patients receiving capecitabine a 4 week washout is required. The trial assessments that should be performed before, during and after pembrolizumab treatment are detailed in section 11.

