17.11.1. Acceptable concomitant medications

All treatments that the investigator considers necessary for a patient's welfare may be administered at the discretion of the investigator in keeping with the community standards of medical care. All concomitant medication will be recorded on the eCRF including all prescription, over-the-counter (OTC), and IV medications and fluids.

All concomitant medications received within 28 days before commencing treatment with pembrolizumab and 30 days after the last dose of pembrolizumab should be recorded.

17.11.2. **Prohibited concomitant medications**

Patients are prohibited from receiving the following therapies:

- Antineoplastic systemic chemotherapy or biological therapy
- Immunotherapy not specified in this protocol
- Investigational agents other than pembrolizumab
- Radiation therapy (except planned loco regional adjuvant radiotherapy)
- Live vaccines within 30 days prior to commencing pembrolizumab and during pembrolizumab treatment. Examples of live vaccines include, but are not limited to, the following: measles, mumps, rubella, varicella, herpes zoster, yellow fever, rabies, BCG, and typhoid (oral) vaccines. Seasonal influenza vaccines for injection are generally killed virus vaccines and are allowed. However, intranasal influenza vaccines are live attenuated vaccines, and are not allowed.
- After commencing pembrolizumab: Glucocorticoids for any purpose other than to modulate symptoms from an event of clinical interest of suspected immunologic etiology. The use of physiologic doses of corticosteroids may be approved after consultation with the Chief Investigator (or designated TMG member).

Patients who, in the assessment by the investigator, require the use of any of the aforementioned treatments for clinical management may need to be discontinued from trial treatment (see section 17.11). Patients may receive other medications that the investigator deems to be medically necessary.

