In prior research no patients with ctDNA detected at baseline spontaneously cleared ctDNA thus it is anticipated that such clearance would demonstrate activity of the intervention. The reference group in the randomised component of the trial will however provide further evidence to support that assertion. The number of patients randomised to the observation group (prior to the implementation of protocol v6.0) who have spontaneous clearance will be recorded and will be presented together with an associated 95% confidence interval to illustrate the likely theoretical upper bound of such an occurrence. Patients who subsequently receive pembrolizumab after transitioning to the non-randomised component of the trial will be excluded from this analysis if they start treatment within 24 weeks of becoming ctDNA positive and are therefore not assessable for the ctDNA clearance endpoint.

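### Adjuvant radiotherapy may run alongside pembrolizumab inside the 24-week clearance window, and no planned analysis separates these patients, so any ctDNA that radiotherapy clears is credited to the drug

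*Protocol*

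**What the plan says.** Surveillance can begin while radiotherapy is still to come or under way: "Patients may start ctDNA surveillance prior to, and during, adjuvant radiotherapy" (Protocol 3.1). The triggering positive sample can therefore precede or fall within radiotherapy. A patient on radiotherapy who is allocated to treatment is offered the option of "or commencing pembrolizumab in combination with radiotherapy" (3.2.1). The v5.0 rationale in 1.2.1 expects this: "In some patients this may result in patients starting pembrolizumab concurrent with adjuvant radiotherapy".

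The eligibility and concomitant-therapy rules agree. The four-week exclusion for prior therapy applies "with the exception of planned loco regional adjuvant radiotherapy" (9.2.2, criterion 3), and the list of prohibited therapies in 17.11.2 reads "Radiation therapy (except planned loco regional adjuvant radiotherapy"). For a patient switching from capecitabine, by contrast, "a washout period of 4 weeks must be observed prior to starting trial treatment" (9.3).

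The therapeutic primary endpoint (19.3.1) is the proportion with neither detectable ctDNA nor recurrence six months after the first dose. It carries no condition on radiotherapy. Section 19.1.2 tests it by an A'Hern single-stage rule in one group that combines the randomised and non-randomised components. After noting that earlier research saw no spontaneous clearance, that section adds "thus it is anticipated that such clearance would demonstrate activity of the intervention".

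Section 19.4 plans an intention-to-treat analysis, a sensitivity analysis in patients who start pembrolizumab, and a split by the v5.0 recruitment windows. None of these splits patients by radiotherapy given during treatment.

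**The concern.** A single-group test has no concurrent comparator, so whatever lowers ctDNA between the first dose and week 24 counts towards the success threshold. For patients irradiated in that window, a second anti-cancer treatment runs alongside the drug. The absence of spontaneous clearance in earlier patients shows that ctDNA does not go away by itself. It does not show what happens during radiotherapy.

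Requiring a positive sample before cycle 1 would not settle this, because radiotherapy can continue after that sample. The observation group does not settle it either. Section 19.1.2 calls it a reference rather than a formal comparator, and the minimisation in 19.2 balanced time to randomisation and capecitabine status, not radiotherapy.

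What is at stake is what a pass means. The count could reach the threshold partly through radiotherapy and still be reported as pembrolizumab activity.

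**Working it through.** **Inputs from the Protocol (19.1.2, row for 30% positivity).** n = 30 treated, p0 = 0.30, p1 = 0.54, 13 successes required, alpha 0.1, power 90%.

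**Inputs not in the Protocol, so assumed.** q is the share of treated patients with radiotherapy in the window: 10%, 20% or 30%. c is the probability that radiotherapy clears a patient who would otherwise not clear: 25% or 50%. d is the true clearance rate due to the drug.

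**Step 1: the plan's own rule.** By exact binomial, P(X ≥ 13 | 30, 0.30) = 0.084 and P(X ≥ 13 | 30, 0.54) = 0.912. With 12 successes the first figure is 0.159, so 13 is the smallest threshold that meets alpha 0.1. The stated rule reproduces.

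**Step 2: observed clearance rate with radiotherapy mixed in.**

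rate = (1 − q)·d + q·[d + (1 − d)·c] = d + (1 − d)·q·c

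**Step 3: a drug exactly at p0 (d = 0.30).**

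| q | c | rate | P(X ≥ 13 of 30) |
|---|---|---|---|
| any | 0 | 0.300 | 8.4% |
| 10% | 25% | 0.30 + 0.70 × 0.025 = 0.3175 | 12% |
| 20% | 50% | 0.30 + 0.70 × 0.10 = 0.370 | 29% |
| 30% | 50% | 0.30 + 0.70 × 0.15 = 0.405 | 44% |

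**Step 4: a less active drug, at the most extreme setting above (q = 30%, c = 50%).**

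| d | rate | P(X ≥ 13 of 30) |
|---|---|---|
| 20% | 0.20 + 0.80 × 0.15 = 0.320 | 12.9% |
| 10% | 0.10 + 0.90 × 0.15 = 0.235 | 1.3% |
| 0% | 0.15 | 0.02% |

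At d = 20% with q = 20% and c = 50%, the rate is 0.20 + 0.80 × 0.10 = 0.28 and the probability is 5.2%. With q = 10% and c = 25%, it is 0.7%.

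**Step 5: a different parameterisation as a check.** Fix the number of irradiated patients, let them clear at 0.5 or 0.7 in total, and let the rest clear at 0.30. Then P(total ≥ 13 of 30) is 0.127 or 0.179 with 3 such patients, 0.183 or 0.326 with 6, and 0.252 or 0.512 with 9. The pattern is the same.

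**Step 6: cost of leaving these patients out of a second readout.** With n = 27 (10% removed), the smallest threshold that meets alpha 0.1 is 12: P(X ≥ 12 | 27, 0.30) = 0.080, and power at 0.54 is 0.883. With n = 24 (20% removed), it is 11: alpha 0.074, power at 0.54 about 0.84.

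**The case against.** **The patients belong in the trial.** Objective 2.1 speaks of clearance "in patients who have completed treatment for moderate or high risk early stage triple negative breast cancer", and a reader might infer that patients still on radiotherapy fall outside it. The Protocol does not support that reading. The trial summary and section 3 describe completed standard therapy as surgery and chemotherapy, and section 3 admits patients before or during radiotherapy. This stands, and it is why the primary set should not be narrowed.

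**The origin of p0 is not stated.** A reader might also infer that 0.30 was derived from patients who had finished all treatment. Section 19.1.2 only calls it an unacceptable rate and gives no source or setting. This stands too, and the point does not depend on where p0 came from.

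**The mechanism and the share are unknown.** Nothing in the Protocol says that loco-regional radiotherapy clears ctDNA. Patients need clear surgical margins (5.4.1) and no macroscopic disease on staging (3.2.1). The share may be small: mutation analysis takes about six weeks (7.1.1), the baseline sample may follow up to four weeks after notification (7.2.2), treatment may start up to four weeks after allocation is notified (9.3), and some positives come at 3 to 12 months. This stands. The assumed values have no anchor in the document, and the bias may be nil. The capecitabine contrast also has limits, since it sets a systemic drug against a local treatment.

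**An inactive drug would not pass.** Step 4 confirms this. Inflation matters only for a drug already clearing roughly 20–30%.

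**The SAP could handle it.** A sensitivity analysis by radiotherapy might well appear there. But the Protocol itself fixes the population, the threshold and the reading of clearance as drug activity, so the limit on that reading belongs in the Protocol.

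**Conclusion.** The concern holds in a limited form. The Protocol lets planned radiotherapy run inside the 24-week window, counts these patients in a single-group test without separation, and attributes clearance to the intervention. If radiotherapy clears ctDNA, the error favours pembrolizumab.

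Its size cannot be determined from the document. Under the assumed shares (10–30%) and added clearance (25–50%), false success for a drug exactly at 0.30 would be about 12% to 44% against a nominal 8.4%. For a drug clearing 10% or less it stays at or below about 1.3%. These figures show sensitivity to assumptions and do not estimate what will happen in this trial.

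It does not follow that the A'Hern test is invalid, that an inactive drug could pass through radiotherapy, or that the primary decision set must be replaced. Moving the primary decision to patients whose radiotherapy ended before the first dose would narrow the stated population. It would also keep those irradiated between the triggering sample and the first dose, so it would not fully remove the problem.

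**What to change.** Keep the primary analysis set. In section 19.4, pre-specify the following:

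1. A sensitivity A'Hern readout that excludes patients with any radiotherapy between the ctDNA-positive trigger sample and week 24, with the threshold read at the resulting n. Allocated patients who never start have no first dose to count from, so the wording should name the date from which their week 24 runs.
2. A separate row showing clearance and adverse events in the excluded patients.

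In section 19.1.2, limit the attribution of clearance to drug activity to a result that holds in both readouts.

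The cost is modest. Radiotherapy dates must be captured on the eCRF, and the sensitivity readout has a smaller n and lower power (for example n = 27, threshold 12, power about 0.88 at p1 = 0.54). No change to the clinical permission for concurrent radiotherapy is proposed.
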